6.3 Early Study Termination Visit

No clinic visit will be planned following termination (withdrawal of consent or PI termination). Participants who stop the study intervention early due to a safety concern will still be followed according to the protocol.

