3. OBJECTIVES AND OUTCOME MEASURES

Table 1 Objectives and Outcomes Measures			
Primary Objectives	Outcome Measures	Endpoints	Analysis
Demonstrate IMR as an acceptable add-on intervention in children with obesity.	1. completion of study Visit 3 (V3) 2. adherence to active IMR 3. participant satisfaction among active IMR participants	1. prevalence of completer status 2. prevalence of IMR completion (actual / planned reps over intervention period) in active IMR group 3. prevalence of agree or strongly agree to question of satisfaction with active IMR	Simple descriptive statistics: calculation of prevalence
Secondary Objectives	Outcome Measures	Endpoints	Analysis
Demonstrate changes in inspiratory muscle functioning and dyspnea reporting following IMR	1. Maximum inspiratory pressure (MIP) 2. Baseline Dyspnea Index score 3. MRC breathlessness scale	1. change in MIP over intervention period 2. change in dyspnea scores over intervention period	Analysis of covariance (ANCOVA)
Demonstrate changes in daily physical activity following IMR	1. moderate-vigorous physical activity (MVPA) time 2. sedentary physical activity (SPA) time 3. total steps	1. change in average daily MVPA time 2. change in average daily SPA time 3. change in average daily step count	Analysis of covariance (ANCOVA)
Exploratory Objectives	Outcome Measures	Endpoints	Analysis
Demonstrate changes in exercise capacity following IMR	1. heart rate during 3 minute step test	1. heart rate change during 3-minute step test	Analysis of covariance (ANCOVA)

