4.10 Study Definition of Completion

Participant study completion will be defined as a participant who has been enrolled and completes Visit 3.

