5.5.3 Study investigator/sponsor decides to withdraw participant

The study investigators or sponsor may decide to take the participant out of this study at any time without consent if:

- Participant's condition changes and the study is no longer in his/her best interest;
- Participant non-compliance with the study protocol;
- The entire study is stopped by the sponsor.

5.5.4 Individual stopping of dosing criteria:

The study investigators will stop treatment of study intervention and the participant will not receive additional doses of study intervention if:

- Participant has a clinically significant severe AE or SAE related to the study intervention;
- Participant becomes pregnant;
- Participant newly meets criteria for study exclusion;
- In the opinion of the investigator, the participant is at significant risk.

If the intervention is discontinued for safety concerns, participants must be followed for safety until 7 days after the last study training session. Participants who are discontinued from study intervention due to an AE, whether serious or non-serious, must be followed by the investigator until the AE is resolved or considered stable.

If any of the above occurs, the participant will be informed, and the investigator will discuss other options.

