5.5.5 Handling of withdrawals

The reasons for withdrawal, or failure to provide a reason, must be documented by the investigator. Reasons for withdrawal may include:

- a. Participant withdraws consent and requests no further follow-up;
- b. Participant does not withdraw consent but withdraws from study intervention;
- c. Study PI/Sponsor decision.

Unless there is complete withdrawal of consent from the participant, every effort will be made to continue follow-up visits.

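### Sections 6.3 and 5.5.5 give opposite rules on visits after a PI-decided withdrawal; following 6.3 can remove Visit 3 outcomes, inflating completer-based satisfaction and lowering the completion rate

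*Combined protocol and SAP*

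**What the plan says.** **Visits after withdrawal.** Section 6.3 reads "No clinic visit will be planned following termination (withdrawal of consent or PI termination" and adds one exception: "Participants who stop the study intervention early due to a safety concern will still be followed according to the protocol". Section 5.5.5 lists three kinds of withdrawal, the third being "c. Study PI/Sponsor decision", and then says: "Unless there is complete withdrawal of consent from the participant, every effort will be made to continue follow-up visits".

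**Grounds for PI withdrawal.** Section 5.5.3 permits withdrawal without the participant's agreement. One listed ground is "Participant non-compliance with the study protocol".

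**Completion and satisfaction.** Section 4.10: "Participant study completion will be defined as a participant who has been enrolled and completes Visit 3". The first primary endpoint in Table 1 is "prevalence of completer status". Section 10.2 takes study completers as the denominator for satisfaction, and section 10.1 sets the target at more than 80%.

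**Where outcomes come from.** In Table 4 the satisfaction questionnaire appears only at Visit 3. MIP, the BDI and MRC scores and the step test are done at Visits 2 and 3, so Visit 3 is their only post-intervention measurement. Follow-up actigraphy is worn in the run-up to Visit 3. Repetitions are recorded automatically by the device and app (4.3).

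**Missing data.** Section 10.5 offers worst-case, baseline or imputation sensitivity analyses, but only if missing data are extensive and judged not random.

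**Safety stops.** Section 5.5.4 says "participants must be followed for safety until 7 days after the last study training session". Section 8.5.1 gives 7 further days from the time the intervention stopped.

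**The concern.** Site staff have two instructions for the same child. If they follow 6.3, a child whom the PI withdraws for poor compliance has no Visit 3, and so no satisfaction rating, no post-intervention MIP, dyspnea or step-test value, and probably no follow-up actigraphy (section 2.3 also asks non-completers to return the tracker).

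The primary question is whether children accept the training. Non-compliance is plausibly related to that, so these losses are unlikely to be random. Satisfaction is the exposed endpoint: a child without Visit 3 is not a completer and leaves its denominator altogether. With 15 children per arm, one or two such cases can move the result across the 80% line.

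**Working it through.** **1. The two rules side by side**

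| Situation | 6.3 | 5.5.5 |
|---|---|---|
| Consent fully withdrawn | no visit | no visits |
| Intervention stopped for safety, consent intact | followed | visits continue |
| PI or sponsor decision (e.g. non-compliance), consent intact | no visit | visits continue |

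Only the last row conflicts, and it includes the non-compliance ground in 5.5.3.

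**2. Inputs for the arithmetic.** The active arm is 15 (4.1), and I take all 15 as having had at least one session. The documents give no PI-termination rate and no figure for this point, so nothing in the plan can be reproduced here. (Table 5 does reproduce as a two-sample t-test, all 24 cells within 0.0005, but does not bear on this point.) I assume k = 1 to 3 children terminated. This matches the all-cause attrition columns of Table 5: 6.7%, 13.3% and 20% of 15 are 1, 2 and 3.

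**3. Satisfaction and completion, worst case.** Suppose S of the 15 are satisfied and the k terminated children are all not satisfied. The completer rate is S/(15 − k), the all-participant rate is S/15, and completion is (15 − k)/15 if there is no other dropout. Exact 95% intervals are in brackets.

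| k | S = 11, completers | S = 12, completers | Completion |
|---|---|---|---|
| 0 | 11/15 = 73.3% (44.9–92.2) | 12/15 = 80.0% (51.9–95.7) | 100% |
| 1 | 11/14 = 78.6% (49.2–95.3) | 12/14 = 85.7% (57.2–98.2) | 93.3% |
| 2 | 11/13 = 84.6% (54.6–98.1) | 12/13 = 92.3% (64.0–99.8) | 86.7% |
| 3 | 11/12 = 91.7% (61.5–99.8) | 12/12 = 100% (73.5–100) | 80.0% |

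The k = 0 row is the all-participant rate. Each lost child adds about 5 to 8 points to satisfaction and takes 6.7 points off completion. The target is passed from k = 2 when S = 11, and from k = 1 when S = 12 (80.0% is not more than 80%).

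**4. Satisfaction when withdrawn children are not all dissatisfied.** With rate r among completers and q among the withdrawn, the bias is r − [r(15 − k) + qk]/15 = k(r − q)/15. For r = 0.85 and k = 2:
- q = 0 gives 11.3 points;
- q = 0.5 gives 4.7 points;
- q = 0.8 gives 0.7 points;
- q = r gives zero.

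**5. Adherence.** No Visit 3 is needed. A bias arises only if terminated children are left out or their planned repetitions are cut at withdrawal. If 13 children are assumed to average 85% and two terminated children 30%, counting all gives (13 × 85 + 2 × 30)/15 = 77.7%, against 85% without the two. Section 10.2 puts completer status in brackets after the adherence endpoint, so which of these applies is unclear.

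**6. Safety stops.** Sections 5.5.4 and 8.5.1 both give 7 days, one counted from the last session and the other from the stop. In 6.3, following such children under the protocol can mean those 7 days, the full visit schedule, or both.

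**The case against.** **6.3 may only mean that no extra visit is added.** Its title allows that reading, and then Visit 3 would stand. But the sentence groups PI termination with consent withdrawal, after which 5.5.1 ends all data collection, and the next sentence keeps follow-up specifically for safety stops. As written, it reads as the end of visits.

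**Acceptability as a whole is biased upward.** A reader might infer this, but the documents do not support it. Losing Visit 3 lowers completion, unless a replacement under 5.5.6 takes the child out of the denominator. Adherence comes from the app, and serious adverse events are counted over everyone with at least one active session.

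**The least adherent children will be removed.** This too goes beyond the text. Section 5.5.3 is permissive, sets no threshold and does not name missed repetitions. The documented response to low adherence is weekly review and encouragement (4.3, 6.2.5). The text shows that such removal is possible, not how often it will occur.

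**The follow-up rules after a safety stop contradict each other.** They do not: a 7-day safety minimum does not forbid later visits. The starting point and extent are ambiguous, no more.

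**The plan already has safeguards.** Section 10.5 targets attrition bias, 10.3 sets a modified ITT population and 10.8 reports dropouts with reasons. These help in part. The trigger in 10.5 is undefined, a tabulation of a few missing children says little about randomness, and a child outside a completer denominator may not register as missing.

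**Any dropout shifts satisfaction in the same way.** This stands. The arithmetic comes from the completer denominator in 10.2, and reconciling 6.3 alone would not change it, so the fix has two parts.

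**Conclusion.** Sections 6.3 and 5.5.5 conflict for a child whom the PI withdraws and who has not withdrawn consent. Following 6.3 means that Visit 3 outcomes can go missing for reasons related to acceptability.

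The consequence is limited to this: completer-based satisfaction can be too high, by about 5 to 8 points per lost child in the worst case, and the completion rate is lowered by 6.7 points per child. The first figure assumes that withdrawn children are not satisfied. The number of children affected is unknown and may be zero. The intervals at n = 15 are far wider than these shifts, but the more-than-80% hypothesis can still change sides on one or two children. Adherence is affected only if its unstated denominator excludes or truncates withdrawn children.

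This is worth correcting, because the conflict is plain and the remedy is cheap.

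**What to change.** 1. Reconcile 6.3 with 5.5.5 so that outcome collection at the already planned Visit 3 is not ruled out for any randomised child who has not withdrawn consent. Leave to the investigator which assessments suit an individual child: 5.5.3 also covers children for whom the study is no longer in their interest, and Visit 3 includes MIP and step testing.
2. In 10.2 and 10.10, also report satisfaction over all active-arm modified ITT participants, with missing counted as not satisfied, beside the completer figure.
3. State the adherence denominator, including how planned repetitions are counted after withdrawal, and whether replaced children stay in the completion denominator.
4. Word 5.5.4, 6.3 and 8.5.1 consistently on where follow-up after a safety stop starts and how far it extends.

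Cost: protocol and analysis-plan wording, one additional summary line, and a few Visit 3 assessments that 5.5.5 already intends. Sample size and schedule do not change.

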6.4 Actigraphy/Physical Activity Assessment

Actigraphy is non-invasive method used to assess cycles of activity and rest over several days to weeks. Actigraphy will be measured using Vivosmart 4 activity tracker, a wrist-band based device that tracks and displays participant fitness activity progress, including steps, floors climbed, calories burned, intensity minutes, oxygen saturation, and heart rate.

Participants will be asked to wear the tracker with the proper fitting (as directed in Visit 1) for at least 7 full days (7 full 24 hour blocks) (max of 14) prior to Visit 2 and at least 7 full days (max of 14) during the week prior to Visit 3.

Participants will be given the safety and product information handout and user's manual from the company that comes with the device. This will include information on battery life and handling, and device precautions.

<https://www.garmin.com/en-US/p/605739/pn/010-01995-13#specs>

6.5 Maximal Inspiratory Pressure (MIP) Measurement

Each participant will be asked to perform five MIP maneuvers, with a goal of matching the highest two within 10 cmH₂O. MIP will be recorded using the PrO2 Fit device. The patient

will be seated for the test. The study staff member will first demonstrate the correct maneuver. The participant will be instructed to exhale slowly and completely, seal lips firmly around the MIP mouthpiece, and then “breathe in as hard as you can, like you are trying to suck up a thick milkshake.” The study staff member will note the largest negative pressure sustained on the pressure reading. The participant will be allowed to rest for about 30-45 seconds and then repeat the maneuver 5 times. This procedure will be completed before and again after the 3-minute step test. The change in best MIP value (post minus pre) will be computed.

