4.3 Study Interventions

Active IMR or SHAM using the PrO2™ device. Each participant will be provided a PrO2™ device and trained on its use as well as its accompanying PrO2 Fit™ app. The PrO2™ is a flow-resistive device that provides inspiratory resistance via a fixed 2mm orifice and has Bluetooth connectivity to most IOS/Android devices or Mac/Windows computers. The PrO2™ device and app allows for both 100% adherence monitoring and immediate user biofeedback.

Participants will be instructed at Visit 1 and Visit 2 to inspire forcefully through PrO2™ until the device signals that the user has achieved the target resistance (via audible alarm and visible light signal). The research team will implement biofeedback signals at a specific inspiratory resistance to provide precise and individualized training target. Successful IMR repetitions will require that subjects achieve a pressure target that is 75% of their MIP.

SHAM intervention. Participants in the control intervention will also use the same PrO2™ device but at a reduced peak resistance of 15% MIP. The research team will implement biofeedback signals at a specific inspiratory resistance to provide precise and individualized training target. Successful IMR repetitions will require that subjects achieve a pressure target that is 15% of their MIP.

Adherence monitoring. All device repetitions are automatically captured and documented via the Bluetooth connection with the PrO2™ app and end-to-end encrypted and transferred to a HIPAA-compliant cloud server (Amazon Web Services). Study staff will review each participant's adherence each week and will provide encouragement as needed.

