6.1 Screening

The investigator will screen participants in accordance with the eligibility criteria detailed previously. Research staff will document applicable informed consent for all participants who satisfy eligibility criteria, and will follow all site policies, procedures and criteria for control of COVID-19.

Participants must satisfy all Inclusion/Exclusion criteria to be enrolled in the active study. Information will be recorded from the clinical medical record or from interview of the participant. The investigator will not exercise selectivity so that bias is prevented.

Table 4 Study Procedures

	Screen visit	Randomization visit	Completion visit
Visit number	V1	V2	V3
Timeline in days (target)	-10-14 ^a	0	42 (40-56)
Consent/assent	x		
Height/Weight/BMI [#]	x		x
Eligibility assessment	x	x ⁵	
Study instructions	x	x	
Actigraphy training ¹	x	x	
PrO2 device/app training		x	
Retrospective Dyspnea scoring ^{##}		x	x
Dyspnea scoring with exercise ²		x	x
Randomization		x	
Maximal inspiratory pressure (MIP) ^{###}		x	x
Stair Step Test		x	x
Adverse event monitoring		x	x
Follow-up actigraphy ³			x
Patient satisfaction questionnaire			x
phone check-ins ⁴	will occur on day (+/- 2) 7, 14, 21, 28, and 35 to assess any problems, encourage adherence and give appreciation for efforts		

1 – worn at least 7 full days (max of 14) prior to randomization

2 – Modified Borg Dyspnea scale and Dalhousie Dyspnea

3 – worn at least 7 full days (max of 14) during week prior to V3; the follow-up actigraphy should occur during the last 14 days.

4 – communication will be made by (IRB approved) mode of participant's choosing including voice call or direct messaging.

5 – assess for eligibility for randomization (tracker adherence, no new exclusions prior to randomization)

a – a date range of 10-14 days prior to randomization is preferred but can be extended up to -28 days. A randomization visit can be scheduled beyond 28 days only at the discretion of the PI.

- should be taken from clinic visit data; may be performed as a research procedure only if needed

- Baseline Dyspnea index (BDI) and MRC Breathlessness Scale

- MIP will be collected before and after the Stair step test

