6.2 Summary of Procedures

6.2.1 Visit 1 (goal timing: day -10 to -14 prior to randomization)

General Visit Description: Eligibility criteria will be confirmed at Visit 1 or via phone call before their visit to the Healthy lifestyle's clinic, if the researcher believes the participant meets eligibility criteria. Research staff will document informed consent from the parent/ guardian in eligible participants.

Participants above the age of 12 years will also provide assent. Eligible participants will receive a Breathe Fit study packet with study handouts and study materials.

Equipment/Supplies needed: Body weight scale, stadiometer, eligibility checklist (printed or electronic), participant informational handouts (for activity tracker accompanying smart device(s) to link with activity tracker).

Anticipated duration: Goal is 30-45 minutes.

Visit 1 Procedures:

1. Confirm eligibility (eligibility checklist).
2. Obtain consent and assent (if child is <12 years old). The consenting process will include instruction about general study details (visits, durations, compensation) and participants will be given a study packet of instructions.
3. Obtain participant demographics, including height, weight, and BMI data (these data should be taken from the electronic health record if already collected). If not obtained during routine care, these data will be collected by research staff.
4. Questionnaires (printed or electronic).
5. Actigraphy training (participants will be given a Vivosmart 4 activity tracker in the correct size and taught on its proper fit and use).
6. Following consent, if all V1 procedures are not able to be completed (due to participant time constraints or family preference), an optional V1a (continuation visit) may be scheduled by phone or in-person home or by follow-up clinic visit.
7. Plan day -7 phone check-in (see phone check-in section below).

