6.2.2 Visit 2 (Day 0)

General Visit Description: Visit 2 will be Day 0, will re-confirm eligibility prior to randomization, will include randomization if eligible and will start the intervention and observation period. Participants must not newly meet any exclusion criteria and must continue to meet all inclusion criteria. Inclusion criteria for randomization will include collection of at least 7 days of valid actigraphy data (confirmed at Visit 2).

Equipment/Supplies needed: Activity tracker (from participant), accompanying smart device(s), printed questionnaires, participant informational handouts, PrO2 trainer, Stair Step Test equipment.

Anticipated duration: 60 minutes.

Visit 2 Procedures:

1. Assessment of baseline actigraphy (participants must have worn the Vivosmart 4 activity tracker for at least 7 full days (max of 14) prior to randomization. If not,

the date of Visit 2 may be extended for an additional 4-14 days for a continuation Visit 2).

2. Questionnaires and eligibility assessment (eligibility checklist, questionnaires can be printed or electronic) (see questionnaires section).
3. Interval history and event monitoring.
4. Measure Maximal inspiratory pressure (MIP) before and after step test (see MIP section).
5. Stair Step Test (see stair step section).
6. Retrospective dyspnea scoring that assesses dyspnea from daily activities (Baseline Dyspnea Index (BDI), the MRC Breathlessness scale), and during the step-test (Modified Borg Dyspnea scale and Dalhousie Dyspnea/Perceived Exertion Scale).
7. Randomization (see the randomization procedure section).
8. Study instruction refresher and questions/answers.
9. PrO2 Fit app and device IMR training.
10. Refresher Training (question and answers) on the use of Vivosmart 4 activity tracker.
11. Discuss plan for phone call visits and future study visit. Plan next phone call check-in visit (Day 7).

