6.2.3 Visit 3 (Day 42) Final In-person visit

General Visit Description: Visit 3 will be on approximately day 42, final assessment of the study. This visit is preferred as an in-person study visit, but may be conducted as an in-home visit if needed (as with Visit 2). Day 42 (+/- 5 days) will be the goal day for study Visit 3. With PI approval, Visit 3 may be conducted up to 14 days away from Day 42, if necessary.

Equipment/Supplies needed: Scale, stadiometer, activity tracker (from participant), accompanying smart device(s), printed questionnaires (or tablet-based REDCap questionnaires), PrO2 trainer (from participant), Stair Step Test equipment, assignment and thank you letter.

Anticipated duration: 60 minutes.

Visit 3 Procedures:

1. Reassessment of participant height, weight, and BMI.
2. Dyspnea scoring assessing daily activities [Baseline Dyspnea Index (BDI), the MRC Breathlessness scale].
3. Dyspnea scoring during the step-test (Modified Borg Dyspnea scale and Dalhousie Dyspnea and Perceived Exertion Scale).
4. Adverse effect monitoring.
5. Measure Maximal inspiratory pressure (MIP) before and after step test.
6. Stair Step Test.
7. Follow up actigraphy (participants must have worn the Vivosmart 4 activity tracker for at least 7 full days (max of 10) during week prior to Visit 3).
8. Patient satisfaction questionnaire.
9. Close out procedures:
 - i. Assignment envelope;
 - ii. Close out letter (i.e. thank you letter).

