7.1.3 Product use and directions

Participants will be instructed to inspire forcefully through PrO2™ until the device signals that the user has achieved the target resistance (via audible alarm and visible light signal). The research team can implement biofeedback signals at a specific inspiratory resistance, which allows for a precise and individualized training target.

At Visit 1: Participants will download the PrO2™ Fit App from the Apple App Store or Google Play. They will be shown how to set up their own PrO2 Fit account and how to connect with their PrO2™ trainer. Research staff will review the planned dosing to start after visit 2. They will be instructed to try to avoid inferring what treatment assignment they have been given, and to not share any impressions they have developed on treatment assignment. The proper use of the trainer will be taught, including safe storage, cleaning and maintenance. Participants will be taught to create an air-tight seal over the mouthpiece after maximal exhalation. The participant will be instructed to breathe in forcefully until the device alarms then continue to maximal inspiration. At Visit 1, participants will be taught on the device while the alarm is set for 15% of their MIP. They will complete a set of 50 repetitions supervised so their technique is assessed and re-direction can occur if needed.

At Visit 2: participants will have refresher training on the use of the PrO2™ Fit app and will repeat their supervised single set of 50 repetitions while supervised to ensure they have the proper technique and the device is working properly.

Research staff will encourage participant and guardian to discuss a plan to optimize adherence to the IMR intervention. This may include picking particular days of the week (e.g. MWF, TuThS) and particular activities to link with IMR (e.g. in mornings before school, evenings before homework, etc.). Guardians will be asked to commit to helping the participant remember their intervention days.

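### Does the post-minus-pre wording for MIP in Section 6.5, or the MIP used at Visit 1 in Section 7.1.3, undermine the six-week MIP analysis?

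*Combined protocol and SAP*

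**What the plan says.** **Measurement.** The Table 4 footnote in Section 6.1 states that "MIP will be collected before and after the Stair step test", and the table marks MIP at Visits 2 and 3 only. The procedure lists for both visits agree; the Visit 3 list reads "Measure Maximal inspiratory pressure (MIP) before and after step test". Section 6.5 describes five maneuvers, repeated after the 3-minute step test, and ends: "The change in best MIP value (post minus pre) will be computed".

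**Outcome and analysis.** Table 1 in Section 3 lists the endpoint as the change in MIP across the intervention period. Section 10.2 lists change in MIP in centimeters of water. Section 10.10 analyses the six-week change by ANCOVA, with the baseline value of the same outcome as covariate. None of these names the pre-step or the post-step set.

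**Visit 1.** Section 7.1.3 says "At Visit 1, participants will be taught on the device while the alarm is set for 15% of their MIP" and, of the same visit, "They will complete a set of 50 repetitions supervised". Section 4.3 is in line with this: "Participants will be instructed at Visit 1 and Visit 2 to inspire forcefully". Table 4, however, schedules MIP and PrO2 training at Visit 2, not Visit 1. The Visit 1 list in Section 6.2.1 begins "Equipment/Supplies needed: Body weight scale, stadiometer, eligibility checklist (printed or electronic), participant informational handouts" and includes no PrO2 trainer.

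**The concern.** The sentence just before the formula in Section 6.5 is about testing before and after the step test. A programmer could therefore read the formula as post-step minus pre-step within a visit. That quantity does not measure a training effect on strength: a gain that raises both sets equally cancels out. Used for hypothesis H2a (that IMR increases inspiratory strength), it would test something else.

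Even if the formula is read as after minus before the intervention, the choice between the pre-step and post-step sets stays open, and the pilot gave different p-values for the two (0.128 and 0.014 in Table 3). With no multiplicity adjustment (Section 10.6), a choice made after seeing results would favour the smaller p-value.

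Finally, if a MIP is taken at Visit 1, there seems to be one more candidate for the ANCOVA baseline, and the Visit 2 value would follow an earlier set of loaded breaths.

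**Working it through.** **1. Check the method against the plan's own power table.** Two-sample t-test, two-sided 5%, equal arms of n, noncentrality d × √(n/2). This gives 0.509 for d = 0.75 at 15 per arm, 0.860 for d = 1.15 at 15 per arm, and 0.833 for d = 1.25 at 12 per arm. All 24 cells of Table 5 reproduce.

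**2. Pilot differences for the two sets (Table 3, IMR versus no IMR).**
- Pre-exercise: 37.0 − 12.5 = 24.5 cmH2O.
- Post-exercise: 14.6 − (−19.0) = 33.6 cmH2O.

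Pooled SDs with the headed 6 and 5 children:
- Pre: √[(5 × 24.1² + 4 × 16.4²)/9] = 21.0, so d = 24.5/21.0 = 1.17.
- Post: √[(5 × 10.5² + 4 × 19.9²)/9] = 15.4, so d = 33.6/15.4 = 2.18.

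Power at 15 per arm is 0.87 (pre) and above 0.99 (post). The printed p-values fit 5 and 4 children (0.128 and 0.013) better than 6 and 5 (0.086 and 0.006). With 5 and 4, d is 1.16 and 2.20, and power to two decimals is 0.86 and still above 0.99.

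**3. The within-visit quantity, if it were used.** Its change between visits is the post-exercise change minus the pre-exercise change:
- IMR: 14.6 − 37.0 = −22.4.
- No IMR: −19.0 − 12.5 = −31.5.
- Difference: −22.4 − (−31.5) = 9.1 cmH2O, which is 9.1/24.5 = 37% of the pre-exercise difference and 9.1/33.6 = 27% of the post-exercise difference.

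Table 3 gives no SD for it. With SD = √(s₁² + s₂² − 2·r·s₁·s₂), where r is an assumed correlation between the two changes:

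| r (assumed) | SD, IMR | SD, no IMR | d | Power, 15 per arm |
|---|---|---|---|---|
| 0.3 | 23.2 | 21.7 | 0.40 | 0.19 |
| 0.5 | 20.9 | 18.4 | 0.46 | 0.23 |
| 0.7 | 18.4 | 14.4 | 0.54 | 0.30 |
| 0.9 | 15.3 | 8.8 | 0.71 | 0.46 |

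This shows what a misprogrammed outcome would cost. It is not a property of the plan, because no section makes this quantity the outcome. It arises only by joining the within-visit reading of Section 6.5 to the six-week time frame of Section 10.10.

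**4. Choosing the set after seeing results.** With two correlated normal test statistics, the chance that at least one exceeds 1.96 in absolute value under the null is 0.083 at r = 0.7 and 0.070 at r = 0.9, against 0.05. It stays at 0.05 if the set is fixed before analysis.

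**5. Which section governs the outcome.** Table 1 and Section 10.10 define the endpoint and its analysis, and they agree. Section 6.5 describes how to perform the test and mentions no hypothesis, endpoint or model. Its formula either restates the six-week change or describes an additional derived variable. Neither replaces the endpoint.

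**6. Which value is the baseline.** Section 10.10 adjusts for the baseline of the outcome variable itself, so naming the set for the change also names the covariate. Section 6.2.2 starts the intervention period at Visit 2, and Table 4 places the first scheduled MIP there. Section 7.1.3 uses MIP at Visit 1 only to set a training alarm.

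**7. Could Visit 1 breaths bias the arms?** Under Section 7.1.3 they come before randomization, with one alarm setting for all. In Section 6.2.2 the Visit 2 MIP is item 4, randomization item 7 and device training item 9. Any familiarization effect on the Visit 2 value therefore falls on both arms alike.

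**The case for a change.** The strongest case for a change is that the pilot has already been described in different ways. Section 2.1 reports a MIP improvement of 34 cmH2O with p = 0.014 without naming the set; the figure matches the post-exercise contrast of 33.6. Table 2 calls the pilot's strength gains non-significant. H2a predicts a significant increase, no multiplicity adjustment is planned, and naming the set would cost a few words. The SAP can choose the analysis version, but it cannot decide what staff do at Visit 1.

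Much of this is true as description. No section names the set, Section 6.5 does not state its reference points, and Sections 7.1.3 and 4.3 do not agree with Table 4 and Section 6.2.1 on Visit 1. Those passages need reconciling as a matter of visit scheduling.

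The step from there to a flaw in the analysis does not follow. Either set, analysed as Section 10.10 says, gives a valid test. The inflation to 7–8% requires a choice made after results are seen, and Section 10.4 puts approval of the SAP before the final analysis. Blinded data alone would not prevent a choice by p-value; the prior SAP does, provided it names the set. The Table 3 footnote shows that this group analysed both sets in the pilot, so reporting both is a foreseeable course.

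**Conclusion.** No change to the plan follows. The endpoint is fixed where it should be, in Table 1 and Section 10.10, and the loose sentence in Section 6.5 does not displace it. The open choice lies between two valid versions of one secondary outcome, with illustrative power of about 0.87 and above 0.99, and the SAP required by Section 10.4 is the ordinary place to settle it. The covariate then follows. The Visit 1 mismatch is an editorial inconsistency in the schedule, and no between-arm bias is shown from it.

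The conclusion rests on the SAP being approved before the final analysis, as Section 10.4 states, and on MIP staying secondary in a study that Section 10.6 calls exploratory. The primary acceptability endpoints are untouched. The pilot figures show scale only: they come from about 9 to 11 children with asthma and a non-sham comparator. The within-visit figures further assume the same children in both Table 3 rows and correlations that the documents do not give.
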